Official title: A Randomized Trial Examining Plasma Exchange using the BD Catheter In an Outpatient Apheresis Unit (REPLACE)

NCT number: NCT04253756 IRB Approved date: 4/22/2020 A Randomized Trial Examining Plasma Exchange using the BD Catheter In an Outpatient AphCresis Unit (REPLACE)

PI: [name] [name], CMSRN, QIA

Faculty Sponsor: [name] MD

Co-Investigator: [name], RN

Research manager: [name] PhD

Date: 11/27/2019

Version: 1

Introduction and Purpose

Nurses and apheresis technicians caring for patients requiring therapeutic apheresis procedures (TAP) utilize a wide range of intravenous catheters to obtain the access required to perform their procedures(Kalantari, 2012), (Golestaneh & Mokrzycki, 2013). The standard of care for our facility is to use an 18-gauge apheresis needle (Medisystems®) for the access site and an 18-gauge autogard catheter for the return site. Unfortunately, there is minimal literature defining best practices for catheter size selection(Salazar et al., 2017). At UT Southwestern Medical Center, our goal is to provide peripheral therapy to reduce the need for central access, such as a medical ports or tunneled catheters(Spires et al., 2018). However, the requirement for an 18 gauge catheter for an adequate return site, at times, rules out the patient for peripheral therapy(Putensen, Leverett, Patel, & Rivera, 2017). This requires central venous access to be obtained, which can delay the start of the procedure.

The lack of scientific evidence to support the use of smaller peripheral return catheters has increased the use of implanted ports in our institution(Putensen et al., 2017). The objectives of our pilot study are patient-centered and include analyzing the safety of using smaller peripheral return catheters without increasing the risk of hemolysis.

Background and Significance

TAP treats a wide range of disease processes and, in all cases, requires inlet and return venous access to perform the procedure. The goal of TAP is to return the patient to baseline and maintain independence and function. A larger needle (18 gauge) can cause more discomfort to the patient as well as additional scarring. A smaller needle may present less discomfort and scarring to the patient. Our goal in our outpatient clinic is to minimize disruption to the patient's routine and help them maintain normal activities of daily living.

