To accomplish these goals, our outpatient clinic is open Monday thru Friday offering 4 different appointment times. All patients that are referred to our clinic for TAP, first receive a vein evaluation to see if the patient is a candidate for peripheral IV therapy. At our clinic, approximately 68% of our TAP's are performed peripherally. This eliminates the risk of a central line infection and any alteration in activities of daily living, such as bathing(Kramer, 2016), (Shang, Ma, Poghosyan, Dowding, & Stone, 2014),(Keller et al., 2018; McDiarmid, 2015).

Our hypothesis, is that the 20-gauge BD Nexiva Diffusics catheter provides the same efficacy as current practice with no increase in adverse events for patients undergoing therapeutic apheresis. The results from our study will be significant because if the 20 guage needle is equally effective for TAP, it can increase the number of patients that would be candidates for peripheral therapy. Therefore, decreasing the need for central venous access, which place the patient at an increased risk of infection. Our study is a comparison of 2 types of infusion catheters. The standard of care is an 18-gauge autogard catheter (control group) which will be compared to the 20-gauge BD Nexiva Diffusics (intervention).

- P patients who require therapeutic apheresis procedures (TAP)
- I use of 20G BD diffusics catheter during apheresis
- C use of 18 G standard of care IV catheter during apheresis
- O no difference in efficacy and no increase in safety events

Concise Summary of Project

This is a randomized pilot study of TAP using the current standard of care catheter (SOC) vs the BD Nexiva Diffusics Catheter. It is a single blinded, randomized study. Data will be used to refine and power a full randomized control trial. For this study, a sample of 33 encounters in each group (total of 66 encounters). Our specific aim is to test the hypothesis that the 20-gauge BD Nexiva Diffusics Catheter provides the same efficacy and lower pain level with no increase in adverse events for patients undergoing apheresis treatments.

Randomization Procedure

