After an eligible participant is consented to the study the patient will be randomized without replacement to the use of one of the two catheters. Using a random number generator, numbers between (1-66) were randomly divided into two groups: SOC Control group and BD Intervention group (Figure 1). A study identification number (SID) key will be saved on a UTSW approved secure device and only the research coordinator will have access to the SID key showing which SID coordinates with each group. This will ensure that unblinding can occur is necessary and there is a backup to randomization.

The research coordinator will have 66 randomized envelops without replacement. Half of the envelops will be assigned to 18G catheter SOC (control) and the other half be assigned to

20G BD Nexiva Diffusics catheter (intervention). The PI will be blinded, therefore the PI will pick an envelope when patients are consented and ready for treatment. Participants will be randomized after they have consented to the study. Participants' will then be randomized to one of the two groups again at each encounter (i.e., SOC visit). Inside the envelope it will tell the investigator if the patient is in the control or intervention group of the study.

To promote a more representative sample, each patient may participate a maximum of 10 times.

Study procedure:

[figure not shown]
Each enrolled patient will participate in the study will be randomized at each encounter. During each encounter the following information will be captured:

- 1. CBC
- 2. Patient discomfort

level with placement of catheter

- 3. Inlet rate
- 4. Return line pressures
- 5. Procedures alarms
- 6. Procedure total time
- 7. Post procedure sample

Treating nurse (RN) will start the TAPs procedure with one of the 2 catheters. During the intervention period, the RN will be at bedside during as it is SOC in the Apheresis unit however for the purpose of this study the RN will have the study data collection form (DCF, Appendix1). The RN will complete the pre-assessment including a pain assessment to establish pain level prior to procedure that is currently documented in the electronic medical record. The patient will be asked to self-report the pain level after the return line has been started on the visual analog scale (VAS) Scale from 0mm to 100mm "0 being the lowest/ no pain, 100mm being the highest

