level of pain". The VAS scale will be used for both the SOC and intervention group to compare the pain level when starting the return line. The RN will collect a CBC before the start of the procedure which will be used in the programing of the TAP procedure. The RN will start recording the "inlet rate, return line pressures, and alarms" every 15 minutes until the procedure is completed.

Before patient disconnects, and after the completion of procedure sing the same therapeutic apheresis procedure access site, a blood sample will be drawn by the RN 2 lavender top tubes (4ml) for plasma hemoglobin test. The plasma hemoglobin test will be sent to the UTSW lab for analysis of hemoloysis and results will be sent back directly to the PI. Blood sample results will be collected by the PI or the study team in an excel spreadsheet (CRF) that will be saved on a secure drive on the UTSW campus.

Hemolysis is defined as the destruction of red blood cells which leads to the release of hemoglobin from the red blood cells into the blood plasma. Each patient will be tested for hemolysis by running plasma hemoglobin test after the procedure has finished. This will be collected in a two lavender tops (4ml) The cost for this test is covered by sponsor and because the patient has an indwelling access to venous blood there will no charge for drawing the sample.. There is no clinical suspicion that the use of the 20-gauge BD Nexiva Diffusics Catheter will increase this risk. Hemolysis will be scored dichotomously as present or absent for each encounter.

Pain is defined as any increase discomfort experienced by the patient associated with the apheresis procedure. The current standard of care is to ask the patient "are you having pain" and then ask them to rate the pain from 0 to 10. For this study, one additional question will be asked after the patient's vein has been accessed (IV catheter in place). The patient will self-report their pain using a 100 mm VAS scale. "*The VAS has been used by healthcare providers to measure the characteristics of disease severity in each patient individually*"(Klimek et al., 2017) Currently, all peripheral apheresis patients have some pain/discomfort while having a treatment, however; it is usually tolerated with minimal complaints.

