efficacy wherein efficacy is represented by 1) the plasma hemoglobin value, and 2) the amount of time (minutes) required to complete a TAP. Hence models will be constructed to compare the mean plasma hemoglobin values by group, and to compare the mean number of minutes to complete TAP by group. Second, ANOVA will be used to compare the mean number of adverse events subjects experience in each group (intervention vs control).

Finally, a planned secondary analysis is to examine if the percent of lumen occupied by the return catheter is associated with return pressures. The suggested standard is that a catheter occupies < 45% of the inner-lumen diameter (measured with ultrasound). Return pressures >400 mm Hg are considered problematic. Chi-square analysis will be used to explore the odds of experiencing a return pressure > 400 mm Hg when the return catheter occupies <45% of the inner-lumen diameter.

Item	Month 1-2	Month 3-6	Month 4-8	Month 9-11	Month 12-18
IRB approval	Х				
Consent/	Х	X			
Enrollment					
Randomization	Х	X	Х	Х	
Data collection	Х	Х	Х	Х	
Manuscript				Х	X
prep					
Study closeout					X

Project Timeline

Enrollment of first patient (month 1), enrollment of the last patient (month 12), completion of data analysis (month 14), and manuscript submission (month 18). The apheresis team see approximatley 3000 TAP treaments each year. Of these, approximately 1500 encounters will meet the primary inclusion criteria. We anticipate that it will take less than 1-year to complete the study.

Future directions

The intention of this pilot study is to test the 20-gauge BD Nexiva Diffusics Catheter performance and efficacy. The findings from this study will be used to provide additional preliminary data to BD to support a National Institutes of Health or Agency for Healthcare Research and Quality (AHRQ) application (pending 2017 AHRQ funding announcements). Stakeholder feedback will be provided through an optional de-identified report to all patients and families.

Presentation of data

It is anticipated that the results from this study will be presented to American Society for Apheresis at their annual convention. The results will also be summarized in a manuscript and submitted for peer-review publication to Journal of Clinical Apheresis.

Appendix 1

Patient Sticker

A Randomized Trial Examining Plasma Exchange using the BD Catheter In an Outpatient Apheresis Unit The "REPLACE" study

Date SID Procedure Type						

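### Hemolysis risk is a stated objective and is scored present or absent, but no cut-off, no by-arm analysis of that score and no pre-procedure value are specified

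*Combined protocol and SAP*

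**What the plan says.** **Objective.** The Introduction and Purpose says that the pilot's objectives "include analyzing the safety of using smaller peripheral return catheters without increasing the risk of hemolysis".

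**Measurement.** The Study procedure section says: "Each patient will be tested for hemolysis by running plasma hemoglobin test after the procedure has finished". Before the procedure, "The RN will collect a CBC before the start of the procedure", and that result is used to program the machine. No plasma hemoglobin is planned at that draw. Appendix 1 has a field for the post-procedure plasma hemoglobin sample and none for an earlier one.

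**Endpoint.** The same section says: "Hemolysis will be scored dichotomously as present or absent for each encounter". It gives no plasma hemoglobin value that separates present from absent.

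**Analysis.** The Statistical Analysis Plan treats plasma hemoglobin as an efficacy measure, for which "models will be constructed to compare the mean plasma hemoglobin values by group". The method is ANOVA, with no covariate named. A second ANOVA compares mean adverse event counts, without saying whether hemolysis is counted. The present/absent score is not mentioned.

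**Design.** There are 33 encounters per group, 66 in all (Concise Summary of Project). "Participants' will then be randomized to one of the two groups again at each encounter", and "each patient may participate a maximum of 10 times" (Randomization Procedure). Plasma exchange, red cell exchange and photopheresis are all eligible (Inclusion Criteria).

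**The concern.** The endpoint that answers the stated objective has no analysis, and the analysis that is specified does not give the quantity the objective asks about. A difference in mean plasma hemoglobin does not tell a reader how many encounters hemolysed on each catheter. It also does not supply the event proportion that a later trial would need for its sample size, although powering that trial is a stated purpose of the pilot. Because no cut-off is fixed, the score as written cannot be reproduced and could be set after results are seen.

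Two features of the measurement add to this. A single value after the procedure cannot separate free hemoglobin released during the procedure from free hemoglobin already there. The three procedures are also pooled. The protocol standardizes inlet rate because the procedures differ in their maximum rates, but makes no such allowance for plasma hemoglobin, although plasma exchange by its nature replaces the fluid being assayed. The documents give no expected values by procedure, so the size of that effect is unknown.

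At stake is a safety conclusion of no increase in hemolysis that would look firmer than the data allow.

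**Working it through.** **The plan's own figure.** 33 + 33 = 66 agrees. No alpha, power, standard deviation (SD), event rate or margin is given, so there is no power calculation to reproduce. For orientation, with independent encounters, two-sided 5% and 80% power, the detectable difference in means is (1.960 + 0.842) × √(2/33) = 0.69 SD.

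**1. Does a missing pre-procedure value bias the comparison?** Catheter type is randomized at each encounter, so pre-existing free hemoglobin is balanced in expectation. A simulation of 20,000 trials, with no catheter effect and half the variance pre-existing, gave a mean difference of 0.001 SD and a type I error of 5.1%. There is no systematic bias.

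**2. Chance imbalance.** The standard error of the difference in starting means is √(2/33) = 0.246 SD, so |difference| > 0.25 SD occurs in about 31% of trials with independent encounters. Repeat patients lower this slightly, because they tend to appear in both arms. The fewest possible patients is 66/10, rounded up to 7 (three with 10 encounters, four with 9). The share of encounter pairs from the same patient is then (3×90 + 4×72)/(66×65) = 0.130. At an assumed intraclass correlation of 0.5, the variance factor is 1 − 0.5×0.130 = 0.935, the standard error is 0.246 × √0.935 = 0.238 SD, and the figure is about 29%. The protocol expects 30 participants, 66/30 = 2.2 encounters each, and the figure then stays close to 31%.

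**3. Effect on the binary score.** Let q be the share of encounters already above the cut-off, assumed to remain above it, and p the true procedure-related risk. The observed risk is q + (1 − q)p, so the observed difference is (1 − q) × the true difference. With p = 3% and 20% (illustrative; neither these nor q are in the documents) and 33 independent encounters per arm:

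| q | Observed risks | Difference (points) | Risk ratio | Exact Fisher power |
|---|---|---|---|---|
| 0 | 3.0% vs 20.0% | 17.0 | 6.7 | 41% |
| 0.1 | 12.7% vs 28.0% | 15.3 | 2.2 | 24% |
| 0.2 | 22.4% vs 36.0% | 13.6 | 1.6 | 15% |
| 0.3 | 32.1% vs 44.0% | 11.9 | 1.4 | 12% |
| 0.5 | 51.5% vs 60.0% | 8.5 | 1.2 | 8% |

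The sizes depend on the assumptions. The direction does not: if the true risks differ, pre-existing positives shrink the observed difference.

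**4. What reporting by arm would show.** The exact two-sided 95% upper limit for 0/33 is 1 − 0.025^(1/33) = 10.6%. For 1/33 it is 15.8% and for 3/33 it is 24.3%. These assume independent encounters.

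**5. What a pre-procedure value would add.** Adjustment multiplies the residual variance by 1 − ρ², where ρ is the pre/post correlation (assumed; not in the documents). At ρ = 0.5 this is 0.75 and at ρ = 0.8 it is 0.36, a cut of 25% to 64%. The detectable difference falls from 0.69 SD to 0.69 × √0.75 = 0.60 SD or 0.69 × √0.36 = 0.41 SD.

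**The case against.** The strongest reply is that randomization makes the comparison of post-procedure means valid without a baseline, that the ANOVA error term already reflects chance imbalance, and that a continuous assay is a legitimate choice for a pilot. All of that stands. The 31% in step 2 is ordinary sampling error at this size and is not in itself a defect. Adjustment for a pre-procedure value would gain precision and attribution; it would not rescue an invalid test.

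A reader might infer three stronger things that the documents do not support:

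- **That pre-existing free hemoglobin counts against the 20-gauge catheter.** It can make a single encounter positive, but each encounter is randomized and both arms carry it equally in expectation.
- **That repeat patients make chance imbalance worse.** With randomization at each encounter they reduce it slightly.
- **That hemolysis risk will never be estimated.** The assay result is kept for every encounter, the plan promises a summary of each variable, and adverse event counts might include hemolysis. What can be said is that no estimate by arm is specified.

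The reply does not answer the gap between objective and analysis. It explains why means may be compared; it does not explain why a present/absent score is defined, left without a cut-off and then not analysed.

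**Conclusion.** The concern holds in this form: hemolysis risk is an objective and a per-encounter binary score is defined, yet the plan gives neither a cut-off nor an analysis of that score by arm. The one analysis of plasma hemoglobin is unadjusted and pools three procedures. Because no pre-procedure value is taken, absolute hemolysis rates cannot be attributed to the catheter.

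The comparison between arms is not biased against either catheter. The costs are lost precision and, for the binary score, dilution toward no difference, which is the outcome the hypothesis predicts. In the illustration the loss runs from 17.0 to 8.5 points as q rises from 0 to 0.5. Even with no pre-existing positives and no events, 33 encounters leave risks up to 10.6% unexcluded. These figures rest on independent encounters and on assumed values of q, p and ρ. That no cut-off and no by-arm analysis are given rests on the text alone.

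This should be changed. It does not invalidate the trial.

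**What to change.** **Needs no new data:**

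1. In the Statistical Analysis Plan, model post-procedure plasma hemoglobin with catheter and procedure type as terms, and allow for repeated encounters within patients, for example with a patient random effect. Procedure type is already on the data collection form.
2. Fix the laboratory cut-off for hemolysis present before the first sample. Report the count and proportion per arm, with a 95% confidence interval for the risk difference that allows for repeated encounters. State whether hemolysis also counts as an adverse event.
3. If no pre-procedure value is added, state that absolute rates are not attributable to the catheter and that pre-existing positives dilute the difference.

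The cost is a short revision of the analysis text.

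**Optional:** measure plasma hemoglobin at the pre-procedure CBC draw and use it as a covariate. Report encounters already raised at baseline separately. Do not define events as new positives only, because an encounter that starts raised and then worsens could never count. The cost is 66 assays, an IRB amendment and possibly up to 8 ml more research blood per encounter (8 + 8 = 16 ml); the documents do not show whether the CBC tube could serve both tests.

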Instructions:	Please complete the following form except for the VAS scale. Must be completed by patient to measure the characteristics of pain severity. Please circle option that apply.					
Collect CBC	Yes	Νο				
Catheter type	18 GA BD Autogard	20 GA BD Nexiva Diffusics				
Vein diameter w/tourniquet:	Vein diameter w/o turniquet:	Vein diameter Procedure Running:				
Asses pain after return placement						
Please rate your current pain by drawing a vertical line across the bar below						

vere		Extremely Severe		
		Procedure d	ata	
tart time:				
Inlet rate	Return line pressures	Alarms	Comments	
	tart time:	tart time: Inlet rate Return line	Procedure da tart time: Inlet rate Return Alarms line	

Total Procedure time:	Procedure en	Procedure end time:		Final Inlet Volume/Blood Processed:	
Collect post proceduer Plasma Hemoglobin	Yes		No		

References

- Golestaneh, L., & Mokrzycki, M. H. (2013). Vascular access in therapeutic apheresis: update 2013. *Journal of clinical apheresis, 28*(1), 64-72.
- Kalantari, K. (2012). The choice of vascular access for therapeutic apheresis. *Journal of clinical apheresis*, 27(3), 153-159.
- Keller, S. C., Williams, D., Rock, C., Deol, S., Trexler, P., & Cosgrove, S. E. (2018). A new frontier: Central line–associated bloodstream infection surveillance in home infusion therapy. *American journal of infection control*, 46(12), 1419-1421.
- Kramer, N. (2016). Monitoring Central Line-Associated Bloodstream Infections (CLABSI) in Home Infusion. *Infusion*, 22(4), 35-44.
- McDiarmid, S. (2015). Reduce the risk of infection by reducing the need for central lines: using ultrasound guidance to establish peripheral access in patients with sickle cell disease undergoing red cell exchange apheresis. *Journal of clinical apheresis*, *30*(2), 98-99.

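### Pain is defined as an increase but measured by one post-placement VAS; the level comparison is usable, and a site-specific prompt, a baseline rating and a planned analysis would sharpen it cheaply

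*Combined protocol and SAP*

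**What the plan says.** The Study procedure section gives the definition: "Pain is defined as any increase discomfort experienced by the patient associated with the apheresis procedure". An increase is a difference between two measurements.

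The measurements described are these.

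- **Before the procedure.** The nurse completes a "pre-assessment including a pain assessment to establish pain level prior to procedure that is currently documented in the electronic medical record". That sentence names no scale. Later in the section, standard care is to ask whether the patient has pain and "then ask them to rate the pain from 0 to 10".
- **After placement.** "The patient will be asked to self-report the pain level after the return line has been started". The scale is stated separately: "The patient will self-report their pain using a 100 mm VAS scale". This is described as one added question, and no VAS is scheduled before access.
- **On the form (Appendix 1).** The patient reads: "Please rate your current pain by drawing a vertical line across the bar below". A line above it ties the assessment to placement of the return line, but the prompt names no site. The form as shown has no field for pain before the procedure.

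The Study procedure section also says that the VAS serves to compare the two arms on pain when the return line is started. That is a level, not an increase. Sources of Research Material gives demographics and diagnosis as examples of record data to be collected and does not name pre-procedure pain. Lower pain with the 20-gauge catheter is part of the specific aim in the Concise Summary of Project. The Statistical Analysis Plan covers plasma hemoglobin, procedure time, adverse events and return pressure, and contains no analysis of pain.

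**The concern.** Two things do not fit together. First, the defined quantity is a change, while the plan obtains one VAS value and, apparently, an earlier rating on another scale. No conversion is planned. Second, the prompt asks for current pain without naming a site. The Introduction describes standard practice as an 18-gauge apheresis needle at the access site plus a return catheter, and the trial varies only the return catheter. The mark may therefore include pain that the randomised device does not affect. The protocol itself says that all peripheral patients have some discomfort during treatment.

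At stake is the pain part of the specific aim. The pilot is also meant to refine and power a full trial, so an effect and SD taken from a loosely defined pain measure would be carried forward.

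**Working it through.** **The plan's own figure.** The design figure is 33 encounters per group, 66 in total. It cannot be reproduced, because no alpha, power, effect or SD is stated. For orientation, at two-sided 0.05 and 80% power the detectable difference is (1.960 + 0.842) × √(2/33) = 0.69 SD. For an assumed VAS SD of 15, 20 or 25 mm this is 10.3, 13.8 or 17.2 mm.

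All SDs, correlations and effects below are assumptions, and encounters are treated as independent. Patients may contribute up to 10 encounters, so the power figures are for orientation only.

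**Step 1: is the level comparison biased?** Write the mark as background pain + access-needle pain + return-site pain. Catheter is randomised at each encounter, so the first two terms have the same expectation in both arms and cancel from the mean difference. In a simulation of 20,000 trials with a true effect of −10 mm, the mean difference stayed between −9.9 and −10.1 mm in every scenario. The post-only difference therefore estimates the same quantity as a difference in increases, apart from floor and ceiling effects.

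**Step 2: what does background pain cost?** Total SD s = √(15² + background SD² + access SD²), SE = s × √(2/33), and power = Φ(10/SE − 1.96).

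| Background SD (mm) | Access SD (mm) | s (mm) | SE (mm) | Standardised effect | Power |
|---|---|---|---|---|---|
| 0 | 0 | 15.0 | 3.7 | 0.67 | 77% |
| 10 | 0 | 18.0 | 4.4 | 0.55 | 62% |
| 15 | 0 | 21.2 | 5.2 | 0.47 | 48% |
| 15 | 10 | 23.5 | 5.8 | 0.43 | 41% |
| 20 | 10 | 26.9 | 6.6 | 0.37 | 33% |

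The loss is in precision, not in the mean contrast.

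**Step 3: when would the contrast itself shrink?** Suppose instead that the patient marks only the worse of the two sites, on a scale limited to 0–100 mm. With inlet and 18-gauge return pain each at mean 35 mm and SD 20 mm, independent, a true 9.3 mm appears as 4.3 mm (4.3/9.3 = 46% retained) and 13.7 mm as about 5.9 mm (43%). Keeping the worse-site rule but letting mean inlet pain run from 15 to 35 mm and the inlet–return correlation from 0 to 0.8, between 37% and 89% of the 9.3 mm is retained. If independent site pains are summed, at least 88% is retained, the loss coming from the scale limit. The documents give neither an inlet-pain level nor a rule for combining sites.

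**Step 4: what would a baseline rating gain?** Assume a 10 mm effect, total SD 20 mm and 33 per arm. With adjustment, the SD is 20 × √(1 − ρ²); for a simple change score it is 20 × √(2(1 − ρ)).

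| ρ (baseline, post) | Post-only | Adjusted | Change score |
|---|---|---|---|
| 0.3 | 52.8% | 56.7% | 40.4% |
| 0.5 | 52.8% | 65.0% | 52.8% |
| 0.7 | 52.8% | 81.2% | 74.6% |
| 0.8 | 52.8% | 92.3% | 89.5% |

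The change score beats the post-only comparison only when ρ exceeds 0.5, so adjustment is the better choice. A pre-access baseline cannot remove access-needle pain, which arises later; only a site-specific question can.

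**The case against.** The strongest reply is that the plan already contains a workable measure: VAS level compared between arms when the return line is started. The form supplies it, and randomisation protects it. On that view the increase sentence is loose wording, and redefining pain as the post-placement level would settle the matter without a second rating. This largely stands. Rewording would remove the contradiction; the baseline rating is a gain in precision, and a small one if the correlation is low.

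Three stronger readings are tempting, and the documents do not support them.

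- **That the measure pulls the arm difference toward zero.** This does not follow from background or access-needle pain being present, as Step 1 shows. A loss of more than half needs the worse-site rule together with inlet pain close to 18-gauge return pain, and it also needs the access needle to be in place at the time of rating.
- **That pain cannot be analysed.** Only the increase on a common scale is unavailable. A crude conversion of the 0 to 10 rating by a factor of 10 could even be formed, though the plan neither proposes nor justifies it.
- **That the form ignores the return site.** Its header refers to return placement. What is missing is the site in the question that the patient answers.

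That the earlier rating uses the 0 to 10 scale is itself an inference from two separate sentences.

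**Conclusion.** The definition and the measurement do not match: no same-scale increase can be formed from what the plan collects. The level comparison can be computed, and under an additive model its mean difference is not biased by other sources of pain. What is lost is precision. In the assumed scenarios, power falls from 77% to 62% with a background SD of 10 mm, and to between 48% and 33% with larger background and access SDs. Attenuation of the contrast is possible if patients mark the worse site, but its size cannot be fixed from the documents. The absence of any pain analysis in the Statistical Analysis Plan is at least as important, because nothing there settles which pain quantity is meant. I rate this a cheap improvement, not a flaw that invalidates the pain comparison.

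**What to change.** 1. On the Data Collection Form, reword the post-placement prompt to ask for pain at the return-catheter site, with the anchors given in Study procedure (0 mm no pain, 100 mm the highest level).
2. Print the same 100 mm bar once more, for overall current pain before any access. At minimum, record the pre-procedure rating already taken as standard care. Do not word the earlier bar as return-catheter pain: no catheter is there yet, so the answers would sit near zero and explain little.
3. Replace the increase definition with the post-placement return-site VAS, compared between arms with adjustment for the pre-access rating. Add this to the Statistical Analysis Plan, for example as a mixed model with the pre-access rating as covariate and a random effect for patient, since patients can contribute several encounters.

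The cost is a revised one-page form, a small IRB update and a few seconds per encounter. The gain depends on the baseline correlation: under the Step 4 assumptions, power rises from 52.8% to 56.7% at ρ = 0.3 and to 65.0% at ρ = 0.5. Overall pre-access pain may correlate only weakly with return-site pain, so the gain from adjustment may be modest. The site-specific wording and the stated analysis are worth having either way.
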